5.1.5 Follow-Up Phase

The follow-up phase begins when the decision is made to discontinue a participant from study treatment (see [Section 8.1](#)), including for AEs, for maximum clinical benefit (investigator decision), for participant request, disease progression, or another reason.

Participants will be evaluated for AEs with visits at 30 days (± 7 days) from the last dose of study drug or can be performed on the date of discontinuation if that date is greater than 42 days from the last dose. Follow-up visit #2 occurs approximately 100 days (± 7 days) after last dose of drug; for details, see [Table 2.-4](#) and [Section 9.2](#). All AEs must be documented for a minimum of 100 days after discontinuation, but drug-related toxicities should continue be followed until they resolve, return to baseline, or are deemed irreversible.

Participants who discontinue treatment for a reason other than disease progression will continue to undergo tumor assessments according to the schedule in [Table 2.-2](#) and [Table 2.-3](#), or earlier if clinically indicated, regardless of subsequent therapy. Introduction of anti-tumor therapy in the absence of progression is strongly discouraged.

Regardless of subsequent therapy, a minimum observation time of 3 years is planned for long-term survivors.

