4.1.2 Expansion Phase

4.1.2.1 Overall Survival for Cohort 1

The primary endpoint of Cohort 1 is overall survival (OS). OS for Cohort 1 is defined as the time between the date of diagnosis and the date of death in Cohort 1. A participant who has not died will be censored at the last known alive date. OS will be followed continuously while participants are on study drug and every 3 months via in-person or phone contact during the survival follow-up phase of the study drug.

4.1.2.2 Progression Free Survival for Cohorts 2 to 5

The primary endpoints of Cohort 2-5 are progression-free survival (PFS).

PFS is defined as the time from first dose to the date of the first documented tumor progression or death due to any cause. Participants who die without a reported prior progression will be considered to have progressed on the date of death. Participants who did not have disease progression or die will be censored at the date of last evaluable tumor assessment. Participants who did not have any on study tumor assessment and did not die will be censored at the first dose date. PFS will be determined by investigators based on RANO criteria. First tumor assessments will occur at week 6 and 12, and will be at every 8 weeks for the first year and then every 12 weeks thereafter until disease progression is documented.

Table 4.1.2.2-1: Censoring Scheme used in Analysis of PFS

Situation	Date of Progression or Censoring	Outcome
No baseline tumor assessments	First dose date	Censored
No on study tumor assessments and no death	First dose date	Censored
Documented progression	Date of the first documented progression per RANO	Progressed
Diagnostic surgical resection without documented progression prior or on the same day and without confirmed disease progression from tumor pathology	Date of last tumor assessment prior to initiation of the diagnostic surgical resection	Censored
No progression and no death	Date of last assessment for disease progression	Censored
Subsequent therapies, including new anticancer therapy, tumor-directed radiotherapy, or tumor-directed surgery received, without progression reported prior or on the same day	Date of last assessment for disease progression prior to initiation of the subsequent therapy	Censored
Death without progression	Date of death	Progressed

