8 CONVENTIONS

The following conventions may be used for imputing partial dates for analyses requiring dates:

For missing and partial adverse event onset dates, imputation will be performed using the Adverse Event Domain Requirements Specification¹². Missing and partial Non-Study Medication Domain dates will be imputed using the derivation algorithm described in 4.3.3 of BMS Non-Study Medication Domain Requirements Specification¹³.

For death dates, the following conventions will be used for imputing partial dates:

- If only the day of the month is missing, the 1st of the month will be used to replace the missing day. The imputed date will be compared to the last known date alive day and the maximum will be considered as the death date.
- If the month or the year is missing, the death date will be imputed as the last known date alive day
- If the date is completely missing but the reason for death is present the death date will be imputed as the last known date alive day

For date of progression, the following conventions will be used for imputing partial dates:

[figure not shown]
- If only the day of the month is missing, the 1st of the month will be used to replace the missing day*.
- If the day and month are missing or a date is completely missing, it will be considered as missing.

*In cases where the date of death is present and complete, the imputed progression date will be compared to the date of death. The minimum of the imputed progression date and date of death will be considered as the date of progression.

For other partial/missing dates, the following conventions may be used:

- If only the day of the month is missing, the 15th of the month will be used to replace the missing day.
- If both the day and the month are missing, “July 1” will be used to replace the missing information.
- If a date is completely missing, it will be considered as missing.

The following conversion factors will be used to convert days to months or years: 1 month = 30.4375 days and 1 year = 365.25 days.

All statistical analyses will be carried out using SAS (Statistical Analysis System software, SAS Institute, North Carolina, USA) unless otherwise noted.

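### A partial start date for later radiotherapy or surgery can be imputed to before the progression it followed, so that a true PFS event is censored

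*SAP*

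**What the plan says.** SAP Section 8 (Conventions) has separate rules for adverse event onset, non-study medication, death and progression dates. Everything else falls to a general default, introduced by "For other partial/missing dates, the following conventions may be used". Under that default, "If only the day of the month is missing, the 15th of the month will be used to replace the missing day"; and "If both the day and the month are missing, “July 1” will be used to replace the missing information".

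Two ordering checks are stated. An imputed death date is compared with the last date known alive. An imputed progression date is compared with death: "The minimum of the imputed progression date and date of death will be considered as the date of progression". No rule shown compares a subsequent-therapy date with progression.

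Medication dates go elsewhere: "Missing and partial Non-Study Medication Domain dates will be imputed using the derivation algorithm described in 4.3.3" of a sponsor specification that is not among the documents. Radiotherapy and surgery are not named in Section 8. SAP Section 7.5.3 lists them apart from systemic drug therapy.

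SAP Table 4.1.2.2-1 makes the order of therapy and progression decisive for PFS. The censoring situation is "Subsequent therapies, including new anticancer therapy, tumor-directed radiotherapy, or tumor-directed surgery received, without progression reported prior or on the same day", and the censoring date is "Date of last assessment for disease progression prior to initiation of the subsequent therapy". PFS is primary in Cohorts 2–5 and secondary in Cohort 1.

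Protocol Section 5.1.5 adds: "Introduction of anti-tumor therapy in the absence of progression is strongly discouraged".

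**The concern.** The general default moves a date to the middle of the month or year whatever else is known about the child. For most variables that is harmless. Here the date decides whether a progression counts, so an error of a few days can replace an event with a censoring at an earlier scan.

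The likely direction is clear. Because the protocol discourages new therapy before progression, most later radiotherapy or surgery should truly follow it. Moving such therapy to before progression removes real events and flatters the drug. With 15, 15 and 10 participants in Cohorts 2, 3 and 4 of each module, a single lost event matters. The SAP already guards the order of death and progression dates; the therapy date, which can cancel an event, has no such guard.

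**Working it through.** **1. Reproduce the plan's figure.** Cohort 2 inputs (SAP Section 5): null PFS(6) 18%, target 38%, one-sided 10%, power 80%, 12 months' accrual, 12 months' follow-up, exponential times.

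- Hazard ratio = ln 0.38 / ln 0.18 = 0.564.
- Events = (1.2816 + 0.8416)² / (ln 0.564)² = 13.8.
- Probability of an event under the target = 0.936.
- N = 13.8 / 0.936 = 14.7, against 15 stated.

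The same approach, with an exact-variance variant, gives 14.0–15.0 for Cohort 3 (stated 15) and 8.8–9.2 for Cohort 4 (stated 10). The model matches the plan closely enough to use below.

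**2. An example.** Progression is on 20 March. Radiotherapy starts on 28 March but only March is recorded. The imputed start is 15 March. No progression is reported by then, so PFS is censored at the last assessment before 15 March. With the true date, 20 March is an event.

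**3. When the order reverses, day missing.** The imputed 15th must fall before progression, so progression must be on day 16 or later, and therapy must fall in the same calendar month. (Progression on the 15th itself counts as the same day and is kept.) In a month of L days with a gap of d days, the qualifying progression days run from 16 to L − d, which is L − 15 − d days. With the mean month of 30.44 days and progression uniform over the calendar:

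P(reversal) ≈ (15.44 − d) / 30.44.

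At d = 15 only the 16th of a 31-day month qualifies; from d = 16 none does. The documents give no gap from progression to therapy, so it is an assumption:

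| Assumed gap | Reversal, day missing |
|---|---|
| Uniform 1–7 days (mean 4): 11.44/30.44 | 38% |
| Uniform 1–14 days (mean 7.5): 7.94/30.44 | 26% |
| Uniform 1–28 days: half of the 1–14 figure | 13% |
| Uniform 1–60 days | 6% |
| Uniform 15–42 days | about 0% |
| Exponential, mean 7 / 14 / 21 / 28 days, rounded up to whole days | 29 / 19 / 14 / 11% |

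**4. When the order reverses, month also missing.** Progression must fall after July 1 and therapy in the same year. There are 183 days after July 1, so P(reversal) ≈ (183 − d) / 365.25. An exponential gap of mean 7 days (about 7.5 once rounded up) gives 175.5/365.25 = 48%. A gap of 6–8 weeks (midpoint 49 days) gives 134/365.25 = 37%.

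**5. Effect of a reversed child on the test.** The one-sample log-rank statistic is Z = (O − E)/√V, where E is the null hazard times total follow-up, and the null is rejected if Z < −1.2816. The visible text does not give the variance form, so the range covers V = E and V = (O + E)/2. A reversed event is taken as censored 1.4 months earlier, about one 6-week scan interval (42/30.44 = 1.38). Simulated one-sided type I error:

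| Cohort | N | None reversed | One | Two |
|---|---|---|---|---|
| 2 | 15 | 7.8–9.1% | 10.5–12.4% | 14.1–16.7% |
| 3 | 15 | 7.6–9.0% | 9.8–11.7% | 12.7–14.9% |
| 4 | 10 | 7.3–9.0% | 10.6–12.9% | 14.8–17.8% |

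For Cohort 2 the null median of 2.25 months used in the SAP test gives nearly the same values as the 18% PFS(6) null. The sample sizes do not change. With an ordering rule in place the reversal probability is zero and the first column of results applies.

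**The case against.** The strongest reply is that the case is narrow and its frequency unknown. A reader might infer that any partial therapy date loses the event. It does not: with the day missing, progression on days 1–15, or therapy in a later month, keeps the order.

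Protocol Section 9.1.2 also allows study drug to continue until progression is confirmed, mentions a 6–8 week interval, and dates a confirmed progression back to its first determination. For children on that path, later therapy would be expected weeks after the dated progression and a missing-day reversal is impossible. This stands. Confirmation is not required in every case, however, so short gaps can occur.

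A reader might take 10–13% as the expected error rate. It applies only once a child has been reversed. Purely for illustration, suppose 50% of 15 children receive radiotherapy or surgery, 10% of those have the day missing, and 13–30% of those reverse. That is 15 × 0.5 × 0.1 × (0.13 to 0.30) = 0.10–0.23 reversals. At about 3 points each on Cohort 2's 7.8–9.1%, the error is about 8–10%, still at or under nominal. Missing months should be rarer still, since survival contacts are every 3 months.

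Nor is the bias strictly one-sided. Therapy on 3 May with progression on 10 May should be censored; imputing 15 May makes it an event. Since such therapy is discouraged, this should be the rarer error, so the net direction holds.

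Three further extensions are not supported:

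- Drug therapy dates follow a specification the reader cannot see.
- The diagnostic-resection row is less exposed, because it does not apply when pathology confirms progression.
- The default is permissive, and its use for radiotherapy and surgery is an inference from the lack of any other rule.

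**Conclusion.** The point holds as a conditional one. Following SAP 8 as written can turn a true PFS event into a censoring, because a default date is allowed to override a documented sequence. This is a rule that can give a wrong result, not merely an omitted detail.

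The size depends on the gap to therapy: roughly one missing-day case in nine to one in three or four (11–29%) if therapy follows within days to a few weeks, and almost none at 15 days or more. Missing-month cases reverse in about 37–48%. One such child is enough to bring the type I error in Cohorts 2–4 to about the nominal 10% or above.

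Cohort 5 has no formal test, so there only the PFS estimate is affected; in Cohort 1 only secondary PFS is. The conclusion rests on radiotherapy and surgery dates using the general default, on the assumed gaps, and on an unstated frequency of partial dates. It does not show that the trial's overall error rate exceeds 10%. It is worth correcting because the correction is simple and can be fixed in advance in an open-label trial.

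**What to change.** Keep the 15th and July 1 as defaults and add to SAP Section 8:

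> If a partial start date of subsequent radiotherapy or tumor-directed surgery is compatible with a start on or after a documented progression in the same recorded month (or year, if the month is missing), the imputed date will not precede that progression, and the progression counts as the PFS event.

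The cost is one sentence and one programming check. A few children whose therapy truly came first will count as events, so PFS may look slightly less favourable.

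Imputing every partial therapy date to the end of its month or year would be the wrong remedy. Children without progression are censored at the last assessment before therapy. Therapy begun in February and dated 31 December would let post-therapy scans count as progression-free time, again favouring the drug.

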9 CONTENT OF REPORTS

All analyses described in this SAP will be included in the Clinical Study Report(s) except where otherwise noted. [REDACTED] Refer to the Data Presentation Plan for mock-ups of all tables and listings.

10 DOCUMENT HISTORY

Table 10-1: Document History

Version Number	Author(s)	Description
1.0	[REDACTED]	Initial version dated 18-Apr-2018
2.0	[REDACTED]	Section 4.2.4 - updated to PFS(6) from PFS(12) to be consistent with table 4-1 of protocol Section 7.2.2- Added “=” to “>=22” in first criteria Section 7.3.2 - Removed baseline pathology (glioblastoma, gliosarcoma) as it is not relevant for this study Section 7.3.6 - Removed “Presence of a measureable lesion at baseline (Yes, No) since this study was not stratified by presence of measurable disease” Section 7.4.1 - Changed dose of ipi from 3 to 1 in formula for relative dose intensity Section 7.5.6 - New Section Section 7.6.10 Added statement regarding use of vendor ULN for ALT and AST [REDACTED]
